### Case study sampling and recruitment

Sampling: We require 39 case study sites across the UK, representing key sampling criteria (e.g. geographical location) that are likely to impact on service delivery. Case study sites will be sub-categorised into three strands:

- i. FCP (n=13)
- ii. FCP has additional qualifications [FCPAQ] (i.e. non-medical prescribing, injecting) (n=13)
- iii. No FCP service is available, physiotherapy provision via a different pathway [PT] (n=13)

In order to achieve a wide geographical sample, case study sites will be selected from England, Wales, Scotland and Northern Ireland. Amongst these, we will also ensure a range of urban and rural environments are included, and a range of sample deprivation based on GP population postcode deprivation index.

We will also record the duration that the service has been established as embeddedness is likely to impact on service outcomes. These will not be selection criteria for the sampling matrix, but the impact of service duration will be explored qualitatively.

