### Recruitment

[figure not shown]
All patients attending their GP practice consulting with an MSKD and meeting the study criteria will be eligible to participate.

In practices with FCP, all new patients consulting the physiotherapist will be provided with a participant information pack by their treating physiotherapist. This pack will include an information sheet explaining the study, contact details of the study team and a consent form with return envelope. Potential participants who require further information will be encouraged to contact the study team to discuss participation. If eligible and willing to participate, they will be required to return the signed consent form to the study team. On receipt of this form, we will contact the potential participant to confirm eligibility, and if eligible will complete the health economics questionnaire (CSRI) over the phone. We will then send a set of outcome measures with a return envelope for completion by the participant. At the participants request we can also provide the outcome measures via email for electronic completion. We will track the number of packs distributed and collect basic anonymised demographic data for all approached patients, enabling us to calculate recruitment rates and report the profile of non-participants. At the end of the data collection period we will also work with database managers in FCP practices to determine the amount of patients who continued to consult their GP for MSKD rather than the FCP, so we can present a descriptive analysis of service engagement. See figure 1.

When the patient consults, the physiotherapist also has the option to provide a recruitment pack and ask whether the patient would like a member of the study team to contact them to explain the study further. For those who would like that, the patient verbally consents to their name and telephone number only being passed to the study team. This will be managed from .nhs to .nhs secure email. The telephone call will simply include further detailing of the study after which the patient can determine whether they would like to participate.

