### Sample size

The aim of this research is to determine that FCP is not substantially worse (non-inferiority analysis) than GP based practice. For the purpose of assay sensitivity, the study is designed as a three arm design which includes usual GP care, FCP and FCPAQ. This sample size computation also accounts for the similarities of patients within each GP centre and treats each GP centre as a cluster within which patients are nested.

Based on Bishop et al (36) a non-inferiority margin of 2 units in SF-36 scale, that is the standard practice is either superior or worse no more than by 2 unit is assumed. Previous research in MSKD, such as Angst et al. (45) has estimated a minimal clinically important difference from 4 points for the SF-36v.2 PCS subscale. The standard deviation of the difference between the SF-36 score between models are assumed to be 6.5 based on Salisbury et al (7). In a one sided 0.05 significance non inferior hypothesis test, to achieve 80% power, 132 subjects are required. To account for the hierarchical nature of the design, i.e. patients are nested within GP centres, this number should be inflated by the design effect.

The design effect for a cluster size of 14 and an intra cluster correlation coefficient (ICC) of 0.0075 (29) will be 1.09, requiring a total sample size to 145 per arm. After allowing for attrition of 20%, the total subjects required per arm is increased up to 181, making the total of at least 13 GP centres per arm, and a per practice sample size of approximately n=14.

It is suggested to randomise 13 GP centres to each physio model and recruit 14 patients with MSKD within each GP centre. In our pilot study, 814 patients consulted with MSKD over 6 months (practice population ~6200). Similar studies in primary care (7, 36) report estimates of 40% of consulting patients being eligible and consenting, we are confident in recruiting the required sample, enabling comparisons between sites and models.

In the analysis, GP centres are included as a random effects in a General Linear Mixed model to account for similarity of patients within each GP centre. The sample size computation was performed using a combination of nQuery 8 and SAS version 9.4 software.

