Primary Outcome analysis: The change in SF-36 Physical Component Score from baseline to 3 months and from baseline to 6 months will be compared between the three service models using a 1-way analysis of variance. If a significant difference is seen, post-hoc unpaired t-tests comparing each pair of service models will be performed in order to determine the superior service model(s). Further comparisons of the three service models will be undertaken in the context of stepwise linear regression modelling, incorporating the demographic and clinical features of the patients, including their baseline SF-36 Physical Component Score. Dummy variables may also be included to represent individual sites. Regression analyses will include multilevel modelling in the form of a general linear mixed model with site as a random effect.

Secondary Outcomes analysis: The change in SF-36 Mental Health Score and in EQ5D-5L Health Related Quality of Life from baseline to 3 months and from baseline to 6 months will be compared between the three service models using a 1-way analysis of variance. If a significant difference is seen, post-hoc unpaired t-tests comparing each pair of service models will be performed in order to determine the superior service model(s).

A similar analysis will be performed for the Roland-Morris Disability Questionnaire score (for LBP patients only) due to the high prevalence and consultation rates for this disorder, for the General Practice Assessment Questionnaire (7, 9-10). For each of the three service models, the proportion of off work patients at baseline who reported having returned to work at 6 months will be compared using a chi-squared test. Costs analysis: Comparisons of costs between the 3 service models will be performed using appropriate statistical tests (according to the distributions of the relevant cost variables).

Health Economics analysis: Initially, we will conduct an analysis of the practice workforce team, and secondly a patient level analysis of outcomes for the sample of MSK patients recruited to the study will be undertaken.

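### The adjusted comparison of service models allows stepwise selection and site dummies although every site belongs to one model only; the planned mixed model should be named as the principal adjusted analysis instead

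*Protocol*

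**What the plan says.** Protocol section 5.3, Data analysis, first compares change in SF-36 PCS between the three service models by one-way analysis of variance with post-hoc t-tests. It then moves to adjustment: "Further comparisons of the three service models will be undertaken in the context of stepwise linear regression modelling", using patients' demographic and clinical features and baseline PCS. Two sentences on site follow. The first is permissive: "Dummy variables may also be included to represent individual sites". The second is a commitment: "Regression analyses will include multilevel modelling in the form of a general linear mixed model with site as a random effect". The Sample size section mentions only the random-effect treatment: "In the analysis, GP centres are included as a random effects in a General Linear Mixed model".

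On the structure of the sites, Case study sampling and recruitment says: "Case study sites will be sub-categorised into three strands", with 13 sites in each. In the Recruitment section, packs at FCP practices are given out by the treating physiotherapist: "In practices with FCP, all new patients consulting the physiotherapist will be provided with a participant information pack". The third strand consists of practices with no FCP service.

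The protocol does not say whether service model is always kept in the stepwise regression, what the selection rule is, or how site dummies and the service-model term would be separated.

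**The concern.** Service model is a property of the practice. No site contributes patients to two models, so there is no within-site information on the contrast of interest. Fixed site effects remove all between-site variation, and that is the only variation from which a service-model effect can be estimated.

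Stepwise selection is a separate difficulty. The Sample size section speaks of randomising ("It is suggested to randomise 13 GP centres to each physio model and recruit 14 patients with MSKD within each GP centre"), but Case study sampling and recruitment classifies practices by the service they already run. The random element there decides only which sites are approached. Control of confounding therefore rests on covariate adjustment. Choosing covariates by p-value can discard a real confounder that happens not to reach the threshold, and the final model's standard errors ignore the selection.

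The stated aim is non-inferiority with "a non-inferiority margin of 2 units in SF-36 scale". That needs an adjusted estimate and a trustworthy interval to set against the margin. A procedure that can drop the service-model term, or report it with an interval that is too narrow, does not reliably supply one.

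**Working it through.** **1. The plan's own figures.** Inputs from the Sample size section: margin 2, SD 6.5, one-sided alpha 0.05, power 80%, cluster size 14, ICC 0.0075, attrition 20%.
- The normal approximation gives 131 per arm; the exact t calculation gives 132 (power 0.802), as stated.
- Design effect: 1 + 13 × 0.0075 = 1.0975. Then 132 × 1.0975 = 144.9, so 145, as stated.
- 145 / 0.8 = 181.25, against a stated 181; 13 × 14 = 182.

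These figures reproduce, and nothing below alters them.

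**2. Rank of the design matrix.** Inputs: 39 sites, 13 per model, each in one model.
- An intercept and 38 site dummies give 39 columns, which span all 39 site indicators.
- Each service-model indicator is the sum of its 13 site indicators, so the 2 model dummies add columns but no rank: 41 columns, rank 39.
- With baseline PCS added: 42 columns, rank 40. A direct check confirms that neither model contrast is estimable.
- Without site dummies (intercept, 2 model dummies, baseline PCS): 4 columns, rank 4, and both contrasts are estimable.

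The shortfall of 2 does not depend on the number of sites: k sites give k + 2 columns of rank k. This step needs no assumption beyond the nesting.

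**3. A subset of dummies.** A dummy for one site fits that site's mean separately, so apart from the covariates the site no longer informs the service-model contrast. The contrast then rests on the unselected sites, and the selection has been made on the outcome.

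The protocol gives no entry rule, so the size of this effect can only be illustrated. Assumptions: forward entry at p < 0.05; 11 completers per site (14 × 0.8 = 11.2); SD 6.5; a true FCP deficit of 2 points, equal to the margin; 1,000 runs per setting. The ICC is the protocol's 0.0075, or 0.05 as an assumed higher value.

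| | ICC 0.0075 | ICC 0.05 |
|---|---|---|
| Service model removable: FCP term absent from final model | 30% | 43% |
| Service model removable: mean estimate when kept (truth −2) | −2.36 | −2.62 |
| Service model held in: mean estimate | −2.00 | −1.98 |
| Service model held in: SD of estimate | 0.96 | 1.27 |
| SD by formula, no site dummies | 0.80 | 0.94 |

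The formula SD is √[2 × 6.5² / 143 × (1 + 10 × ICC)] with 13 × 11 = 143 completers per arm: √(0.591 × 1.075) = 0.80 and √(0.591 × 1.5) = 0.94. With the term held in, the SD is therefore larger by a factor of 0.96 / 0.80 = 1.20 or 1.27 / 0.94 = 1.35.

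**4. How much is due to the dummies.** A second simulation (the same completers, SD and entry rule, 8 added noise covariates, 400 runs, Monte Carlo standard error about 2.3 points per figure) compared retention of the 2-point deficit without and with site dummies. Retention was 77% against 69% at ICC 0.0075, and 75% against 65% at an assumed ICC of 0.03. The dummies cost 8 to 10 points. The 23% to 25% lost without them is ordinary significance selection.

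**The case against.** The strongest reply is that the protocol already contains most of the cure. The sentence straight after the one on dummies commits to a mixed model with site random, and the Sample size section names only that treatment. The dummies are optional. A reader might infer that the plan can return no adjusted service-model effect at all; the documents do not support that, because the mixed model keeps both contrasts estimable. This part of the reply stands and limits the weight of the point. It does not remove it: the mixed model is added to the regression analyses, is not called principal, and leaves stepwise selection and the dummies in place.

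Second, full collinearity would be seen on fitting, since software flags or drops aliased terms. That is true. The less visible problem is a selected subset.

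Third, a reader might infer from the simulation that sites would take over the service-model effect. That depends on service model being a removable candidate, which the protocol does not say. If the term is always kept, the estimate stays near −2 on average and the cost is precision. Nor is the share of runs in which some site dummy enters (about 90% at ICC 0.0075) a measure of absorbed effect: 38 independent null candidates at 5% would give 1 − 0.95³⁸ = 86%.

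Fourth, a ban on site fixed effects anywhere would go too far. The protocol also wants to compare sites, and dummies are legitimate for describing sites or comparing them within one model.

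Finally, selection rules are often left to a statistical analysis plan. Here, though, the protocol itself names stepwise selection and permits the dummies, so the text can be judged as written. The leading analysis of variance is not affected by this point.

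**Conclusion.** The point holds in a limited form. It is certain, given the nesting, that a full set of site dummies makes both service-model contrasts inestimable. It is also sound that p-value-driven covariate selection is a poor basis for adjustment in a non-randomised comparison and leaves nominal standard errors and p-values unreliable. Neither the loss of interval coverage nor the bias from omitted confounders was quantified.

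The simulated figures are illustrative only, because they rest on an entry rule, a completer count and, in part, a removable service-model term that the protocol does not specify. They indicate a loss of precision (SD up by a factor of 1.20 to 1.35) if the term is kept, and a material chance of losing it if it is not, with only part of that chance due to the dummies.

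The protocol's mixed model is sound on this point. The defect is that weaker alternatives remain permitted beside it with no stated order of precedence. This should be corrected, but it does not undermine the design.

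**What to change.** In the primary outcome paragraph of section 5.3, Data analysis:

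- Delete the word *stepwise*.
- Replace the sentence on dummy variables with a statement that site dummies are not fitted alongside the service-model term, and may be used only to describe sites or to compare sites within one service model.
- Name the mixed model already planned as the principal adjusted analysis. Service model is a fixed effect that is always included, the covariates are pre-specified and all retained (baseline SF-36 PCS among them), and site is a random intercept.

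The service-model comparison then rests on 39 − 3 = 36 between-site degrees of freedom. The change costs wording only: no extra data, sites or patients, and the stated sample size is unchanged.

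### The secondary-outcome text lets any one of four tests (up to eight by inference) name a superior service model, with no design basis for such claims

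*Protocol*

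**What the plan says.** The Data analysis section of Work Package 3 (protocol section 5.3) treats the secondary outcomes as follows.

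- **SF-36 mental score and EQ-5D-5L.** "The change in SF-36 Mental Health Score and in EQ5D-5L Health Related Quality of Life from baseline to 3 months and from baseline to 6" (in months) is compared across the three models by 1-way ANOVA. If that is significant, "post-hoc unpaired t-tests comparing each pair of service models will be performed in order to determine the superior service model(s)." The primary outcome paragraph just above uses the same rule for the SF-36 physical score.
- **Roland-Morris and GPAQ.** "A similar analysis will be performed for the Roland-Morris Disability Questionnaire score (for LBP patients only)," and the same sentence continues "for the General Practice Assessment Questionnaire (7, 9-10)." The intervals and the superiority purpose are not restated.
- **Return to work.** "the proportion of off work patients at baseline who reported having returned to work at 6 months will be compared using a chi-squared test." There is no post-hoc step and no mention of a superior model.
- **Costs.** "Comparisons of costs between the 3 service models will be performed using appropriate statistical tests," with no number of tests given.

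No significance level is attached to any of these tests. The only level in the protocol is in the Sample size section: "In a one sided 0.05 significance non inferior hypothesis test, to achieve 80% power, 132 subjects are required." That section gives the aim as showing that FCP is not substantially worse than GP-based care, with a margin of 2 SF-36 units.

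**The concern.** The protocol labels these outcomes secondary but fixes the same inferential purpose for them as for the primary. Followed as written, a significant ANOVA on one secondary score at one visit is enough to name a superior model. Nothing in the paragraph makes this depend on the primary result.

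ANOVA followed by t-tests keeps the error near its nominal level within one outcome at one visit when all three models are equal. It gives no protection across several outcomes and two visits.

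The protocol's Summary says results will be used to build a commissioning pack. A chance difference on a single score could therefore be passed on as evidence that one service model is better. The study was sized to support a non-inferiority statement on the SF-36, not superiority statements on other measures.

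**Working it through.** **What the design was sized for.** The stated figures come from a non-inferiority comparison on the SF-36: margin 2, SD 6.5, one-sided 0.05, power 80%, cluster size 14, ICC 0.0075, attrition 20%.

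- Per arm, normal approximation: 2 × 6.5² × (1.645 + 0.842)² / 2² = 130.6, so 131. The noncentral t distribution gives 132, as stated.
- Design effect: 1 + 13 × 0.0075 = 1.0975 (stated as 1.09). 132 × 1.0975 = 144.9, so 145, as stated.
- Attrition: 145 / 0.8 = 181.25 (stated as 181).

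The sample size is reproduced, and no secondary outcome enters it. The protocol gives no error rate for the secondary tests, so there is no further figure to reproduce.

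**Counting the tests that carry the superiority rule.**

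| Outcome | Intervals | Tests | Basis |
|---|---|---|---|
| SF-36 mental score | 3 and 6 months | 2 | explicit |
| EQ-5D-5L | 3 and 6 months | 2 | explicit |
| Roland-Morris (back pain only) | both, if carried over | 2 | by inference |
| GPAQ, as one score | both, if carried over | 2 | by inference |
| Return to work | 6 months | 0 | no superiority wording |

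That gives four explicit tests and at most eight.

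**Chance of at least one false finding.** Assumptions: the three models are identical and each ANOVA is run at 5%, a level the protocol does not state. If the tests are independent, the chance is 1 − 0.95^k:

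- k = 4: 1 − 0.95⁴ = 18.5%
- k = 8: 1 − 0.95⁸ = 33.7%

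Correlation lowers these figures. I simulated each three-group test as a 2-df chi-square statistic with critical value 5.99, using one common correlation between all tests (400,000 draws). The correlations are assumptions; the protocol gives none.

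| Correlation | 4 tests | 8 tests |
|---|---|---|
| 0 | 18.6% | 33.7% |
| 0.3 | 17.5% | 30.3% |
| 0.5 | 15.7% | 25.6% |
| 0.7 | 13.4% | 19.7% |
| 0.8 | 11.8% | 16.3% |

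**Does a significant ANOVA lead to a named model?** With equal arms and a common variance, the three squared pairwise t statistics sum to 1.5 times the chi-square, so at least 1.5 × 5.99 = 8.99. The largest is at least half of that sum, 4.49, which exceeds 1.96² = 3.84. A significant ANOVA therefore yields at least one significant pair. Because the t-tests run only after a significant ANOVA, they cannot raise the rate when all models are equal. The figures above are therefore rates of falsely naming a model.

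**Cross-check.** A patient-level simulation of the eight ANOVAs used 13 practices per arm and assumed 11 analysed patients per practice and 30% with back pain (3,000 runs per setting). It gave 33% with no correlation, 29% with correlations of 0.3 between outcomes and 0.6 between visits, and 27% with 0.5 and 0.7. With an ICC of 0.0075 that the ANOVA ignores, the last two became 35% and 31%. Clustering can thus push the rate slightly above the table's upper end.

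**The case against.** **The gap belongs to the SAP.** The absence of a multiplicity rule, a test order or an exploratory label is commonly left to the SAP. The health economics text refers to a statistical plan that is not shown. This stands, and the absence is not the point here. What remains is a purpose that the protocol itself fixes: an SAP calling these outcomes supportive would contradict this paragraph.

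**The outcomes are already ranked.** One primary outcome is named and the others are labelled secondary. That is true, but the rule attached to them is the primary's rule.

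**The consequence is limited.** No passage makes a single p-value trigger a recommendation. Quantitative results are to be integrated with qualitative and economic data, and a cost-consequences analysis is planned. This also stands and keeps the point modest. It does not remove the wording that names a superior model.

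**Stronger readings that the protocol does not support.**

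- A reader might count nine tests, each naming a superior model. Return to work has no such step, and Roland-Morris and GPAQ inherit it only by inference.
- A reader might multiply the count by testing each GPAQ domain. The outcome table lists several domains, but nothing says they are tested separately.
- A reader might say each test is run at full alpha. No level is stated for these tests.
- A reader might call a false claim likely. Every figure above is below one half.

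**Conclusion.** The point holds as one of wording. The protocol applies the primary's superiority rule to secondary outcomes, explicitly in four tests and by inference in up to eight. If the models are identical, the chance of at least one false superior model is about 12–19% for four tests and 16–34% for eight. This rests on an assumed 5% per test, a common correlation from 0.8 down to 0, both intervals carrying over for Roland-Morris and GPAQ, and GPAQ being a single score. Even the smallest figure is more than twice 5%. The protocol does not promise control of error across secondary outcomes, so the figures describe what the wording permits and do not show that a stated guarantee is broken.

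The superiority claims also have no stated design basis, because the aim is non-inferiority and the sample size concerns the SF-36 only. The primary analysis is unaffected by this point. Its own superiority wording also sits uneasily with the non-inferiority aim, but that is a separate matter which this change does not settle. I rate this a cheap improvement.

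**What to change.** In the Secondary Outcomes paragraph of the Data analysis section:

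1. End the sentence on post-hoc t-tests before its purpose clause, so that it no longer says that the tests serve to identify a superior model.
2. State that the secondary outcomes are supportive, and that this includes Roland-Morris and GPAQ.
3. Report each FCP model's difference from usual GP care as an estimate with a 95% confidence interval, with no superiority claim.

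I would not make a Holm adjustment or a gate on the primary result part of this fix. Both are debatable trade-offs, and the gate would depend on a non-inferiority test that the Data analysis section does not specify.

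The cost is a change of wording, with no new data or patients. The downside is that an isolated secondary difference can no longer be presented as showing that one model is superior.

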### Data analysis

The quantitative data generated in this work package will be integrated with data from the realist qualitative interviews across sites (see sub-section 7). The realist evaluation process will adhere to the recently developed RAMESES II reporting standards for realist evaluation (2) as well as quality guidelines and training materials for realist evaluation that are publicly available at www.ramesesprojects.org.

Quantitative: Summary statistics will be compiled as follows by site: (i) Recruitment/Retention: Recruitment duration (start and finish date), number of patients eligible (according to study criteria) during this time, number of eligible patients approached, number of patients agreeing to participate and then completing baseline assessment, number of patients achieving completion (with accompanying inclusion rates), and date of baseline measurements for first and last completed patient. (ii) Demographic/Diagnostic: Descriptive statistics (numbers, means, standard deviations, medians, ranges, proportions as applicable) will be tabulated for all demographic and clinical features, along with number of days from baseline assessment to 3 months and to 6 months assessment. We will retain participants who fail to complete 3-month outcome measures, but complete the 6-month primary endpoint data collection. All of these summary statistics will also be accumulated across the three service model groups and in total.

Statistical comparisons will be performed as follows: Drop-out analysis: The overall drop-out rates across each of the three service model groups will be compared using a chi-squared test. The demographic and clinical features of the three groups will be compared in order to establish possible reason(s) should a statistically significant difference be seen in drop-out rates, and to be aware of inequalities between the three groups in preparation for their comparison for outcome measures.

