The analysis of the individual patient level data will be reported as a cost-effectiveness analysis using the primary outcome, SF-36 PCS, and will also be presented as a cost utility analysis, using the data collected from the EQ-5D-5L for the elicitation of the required QALY information. Details on how costs and outcomes will be gathered and the economic analysis plan, are given above. Adjustments will have to be made for any baseline variations in patient characteristics, if these are identified during the analysis. Differences in accrued QALYs between the groups will always be estimated whilst controlling for differences in baseline EQ-5D scores. The structure and type of regression model employed will be determined by the data collected and available for analysis. Given the multi-level analysis being undertaken within this study, as detailed within the statistical plan, any differences identified between any of the service models with regard to costs and/or health outcomes will be explored by an appropriate regression analysis. The base case economic analysis will adopt a direct NHS resource use cost perspective. The sensitivity analysis will explore whether or not a broadening of the analysis to a more societal perspective through the inclusion of patient out-of-pocket expenditures and productivity effects has any impact the economic conclusions.

A cost-consequences analysis will also be conducted to enable the full range of outcomes and costs, and how these are distributed across stakeholders, to be taken into consideration.

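### MCS, EQ-5D-5L and Roland-Morris are compared only by unadjusted ANOVA and t-tests on change; baseline adjustment is specified only for PCS and QALYs, and the practice random effect is specified only for PCS

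*Protocol*

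**What the plan says.** All references are to the protocol, section 5.3 (Work Package 3).

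- **Outcome Measures, Table 2.** MCS, EQ-5D-5L and Roland-Morris (low back pain patients only) are each collected at 0, 3 and 6 months, so each has its own baseline score.
- **Data analysis, Secondary Outcomes analysis.** The quantity compared is "The change in SF-36 Mental Health Score and in EQ5D-5L Health Related Quality of Life from baseline to 3 months" and to 6 months, by one-way ANOVA. If that is significant, "post-hoc unpaired t-tests comparing each pair of service models will be performed in order to determine the superior service model(s". For the back pain measure, "A similar analysis will be performed for the Roland-Morris Disability Questionnaire score (for LBP patients only".
- **Data analysis, Primary Outcome analysis.** PCS starts with the same ANOVA and t-tests. It then also gets regression on patient features, "including their baseline SF-36 Physical Component Score", and a general linear mixed model with site as a random effect. The secondary paragraph has no such step.
- **Data analysis, Health Economics analysis.** "Differences in accrued QALYs between the groups will always be estimated whilst controlling for differences in baseline EQ-5D scores".
- **Sample size.** The calculation inflates for patients nested in GP centres and says that centres enter the analysis as random effects.

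**The concern.** Subtracting the baseline score is not the same as adjusting for it. A change score fixes the coefficient on baseline at 1, whereas the coefficient that best predicts follow-up is usually smaller. Two consequences follow.

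The first holds whatever the baseline balance: the change score carries more residual variance than it needs to, so the secondary comparisons are less precise than the data allow. Ordinary ANOVA and t-tests also treat patients from one practice as independent, which the Sample size section says they are not.

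The second is conditional. If mean baseline scores differ between models and all groups regress towards a common mean, the group that starts worse improves more with no service effect at all. Baseline gaps are plausible. Sites are categorised by the model they already run. FCP sites come from the survey database and non-FCP sites from the research network. Packs are handed out by the physiotherapist in FCP practices and by GPs or reception staff elsewhere. At stake is which model is named superior on mental health, quality of life and back pain disability. One instrument, the EQ-5D-5L, could also read differently in the clinical and economic results for analytic reasons alone.

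**Working it through.** **1. The protocol's own figures.** Margin 2, SD 6.5, one-sided 5%, 80% power: 2 × (1.645 + 0.842)² × 6.5² / 2² = 130.6, so 131 against 132 stated. Design effect 1 + (14 − 1) × 0.0075 = 1.0975; 132 × 1.0975 = 144.9, the stated 145. With 20% attrition, 145 / 0.8 = 181.25, stated as 181. These agree to rounding. They concern PCS; no figure is given for the secondary outcomes. I use 145 as the number analysed per arm.

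**2. Assumptions.** The protocol gives neither the baseline to follow-up correlation (ρ) nor any baseline gap (d, in SD units). I take ρ = 0.5 to 0.7, d = 0.2 or 0.3, and equal variances at both times.

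**3. Precision.** In units of the score variance, the residual variance is 2(1 − ρ) for change and 1 − ρ² with baseline adjustment. Their ratio is 2/(1 + ρ).

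| ρ | Change | Adjusted | Ratio |
|---|---|---|---|
| 0.5 | 1.00 | 0.75 | 1.33 |
| 0.6 | 0.80 | 0.64 | 1.25 |
| 0.7 | 0.60 | 0.51 | 1.18 |

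The change score has 18% to 33% more residual variance. Equivalently, adjustment removes 15% to 25% of it.

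**4. Clustering.** If the design effect of 1.0975 also applied to these outcomes, a two-sided 5% test that ignores it would have an effective critical value of 1.96 / √1.0975 = 1.871, which is a true error rate of about 6.1% with no baseline gap.

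**5. False differences under regression to a common mean.** With no true effect, the expected difference in change is (1 − ρ)d. Its standard error is √(2(1 − ρ)) × √(2 × 1.0975/145). A two-sided 5% pairwise test with that standard error rejects with probability P(|N(bias/SE, 1)| > 1.96).

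| ρ | SE | Bias, d = 0.2 | Rejects | Bias, d = 0.3 | Rejects |
|---|---|---|---|---|---|
| 0.5 | 0.123 | 0.10 | 12.8% | 0.15 | 23.0% |
| 0.6 | 0.110 | 0.08 | 11.2% | 0.12 | 19.3% |
| 0.7 | 0.095 | 0.06 | 9.6% | 0.09 | 15.7% |

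The three-arm ANOVA with one arm shifted, clustering ignored, behaves much the same: 12.9%, 11.2% and 9.6% at d = 0.2. With d = 0 there is no bias.

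**6. Roland-Morris.** Only back pain patients contribute. If they are a third to a half of each arm (an assumption: 48 to 72 patients), the 12.8% cell falls to about 7.5% to 8.8%. The bias in SD units is unchanged.

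**7. The reverse case.** Suppose instead that the groups have stably different means. Change is then unbiased, and the baseline-adjusted contrast is biased by the same (1 − ρ)d, with the smaller standard error √(1 − ρ²) × √(2 × 1.0975/145). It rejects 15.5%, 12.8% and 10.5% of the time at d = 0.2, and 29.1%, 23.0% and 17.6% at d = 0.3, for ρ = 0.5, 0.6 and 0.7.

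**The case against.** **Baseline adjustment is not wholly absent.** A reader might infer that these outcomes are never adjusted for baseline. That is too strong. EQ-5D-5L data are adjusted when they enter as QALYs. The economic section adds "Adjustments will have to be made for any baseline variations in patient characteristics, if these are identified during the analysis", and says that differences between models "with regard to costs and/or health outcomes will be explored by an appropriate regression analysis". This stands against the broad reading. It does not repair the secondary analysis: the text sits in the economic section, is conditional, and names no covariates for MCS or Roland-Morris.

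**The EQ-5D sentence is about QALYs.** A reader might infer that the protocol contradicts itself. It does not. A QALY total accumulates utility over follow-up, while the change score has already subtracted baseline. These are different quantities, so this is an uneven approach to one instrument.

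**Imbalance is not forecast.** A reader might infer that the protocol expects unequal groups. It says only that features are compared "to be aware of inequalities between the three groups in preparation for their comparison for outcome measures". That is a check, and no gap is given anywhere.

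**Adjustment can itself mislead.** This is the strongest objection, and it stands. Step 7 shows that with stably different populations the adjusted model is the biased one, and by the stated inputs it rejects more often than the change score does under step 5. The documents do not settle which case applies. The Sample size section speaks of randomising centres, but the sampling and recruitment text describes sites chosen by their existing model, with randomness only in which sites are approached. The measures called baseline are also completed after the first consultation, so the service may already have touched them. The change score uses that same baseline.

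**These are secondary outcomes, and detail may sit in an analysis plan.** The first part limits the weight of the point. The second does not remove it, because the protocol names the tests.

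**Conclusion.** The point holds in a limited form. The protocol fixes unadjusted tests on change for MCS, EQ-5D-5L and Roland-Morris, and states a baseline-adjusted mixed model with a practice effect only for PCS. Two costs do not depend on baseline imbalance: 18% to 33% more residual variance than needed (ρ assumed 0.7 to 0.5, equal variances), and an analysis that ignores practice although the Sample size section says that centres are random effects.

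The false-positive risk is conditional. It is about 10% to 13% at an assumed 0.2 SD gap with 145 per arm, and only if the groups regress to a common mean. It is smaller for Roland-Morris. It should not be read as an established error rate of the planned tests, nor as proof that adjustment removes bias here. The change is worth making, but it does not touch the primary conclusion.

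**What to change.** In the Secondary Outcomes analysis paragraph, make the mixed model already named for PCS the main analysis for MCS, EQ-5D-5L and, in back pain patients, Roland-Morris. The outcome is the 3- and 6-month score. The fixed effects are service model and the baseline score of the same measure. Practice is a random effect. Report the contrasts between models with confidence intervals.

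Keep the change-score comparison as a sensitivity analysis. State that baseline adjustment in non-randomised groups assumes a common mean and does not remove other confounding, so that a disagreement between the two analyses is reported and discussed.

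The cost is a change of wording and a small amount of extra analysis. The baseline scores are already collected, and a patient without one is lost to the change score too.
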